6.1 Inclusion criteria

Child participants:

- Inpatients (or child awaiting surgery on pre-operative ward) in Great Ormond Street Hospital
- Aged 0 - 59 months
- Clinically stable (as judged by the ward sister and medical team)
- Guardian (parent or adult with legal responsibility for the child) present
- Written informed consent from the guardian

Healthcare providers:

- Healthcare provider employed at Great Ormond Street Hospital who are trained in the use of pulse oximetry
- Written informed consent from the healthcare worker

6.2 Exclusion criteria

Child participants:

- Unstable or critically unwell patients (as judged by the ward sister and medical team)
- Parents (or adult with parental responsibility) who are not able or willing to give informed consent
- Parents (or adult with parental responsibility) unable to speak English well enough to understand study methods or consent form
- For part (2) of the study (usability of the probe by healthcare workers), patients with oxygen saturation 95% or below will be excluded

Healthcare providers:

- Healthcare provider who are not trained to use a pulse oximeter
- Healthcare provider who have not given written informed consent

7 Recruitment

Child participants:

Recruitment of children will be purposeful; to ensure a range of ages (0-59 months old) are included in the study. Children will be recruited from inpatient wards at GOSH, by the clinical researcher with the assistance of the ward sister. We will ask the ward sister to identify patients in the four different age categories who are stable and whose parents (or adult with parental responsibility) are present on the ward. We will ask the ward sister to hand out patient information leaflets to the guardian, and the research team will only approach potential participants if they are happy to be approached. Basic patient demographic data will be collected from the electronic patient notes. Data from other sources will not be required.

Healthcare providers:

Recruitment of healthcare providers will be purposeful, to ensure a range of experiences with pulse oximetry are included in the study. Any nurse employed at Great Ormond Street Hospital who is trained to use pulse oximetry will be eligible to participate in the study. We will approach nurses on each ward in the hospital and hand out study healthcare worker information. Any nurse who is willing to participate will be asked for informed consent.

8 Study procedures and schedule of assessments

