8.1 Informed consent procedure

It is the responsibility of the clinical researcher to obtain written informed consent from each subject prior to participation in the study, following adequate explanation of the aims, methods, anticipated benefits and potential hazards of the study. No study procedure will be conducted prior to taking consent from the participant. Consent will not denote enrolment into the study. The signed consent form will be retained at the study site and a copy placed in the medical notes.

Child participants:

A member of the research team will approach the responsible clinical team for potential participants. Having identified a potential patient, the nurse responsible for the patient will make the initial approach to the child and provide the guardian with an information sheet. Only after this point will a member of the research team then approach the parent to ask for informed consent, provided the parent is happy to be approached, making it clear that participation will have no impact on the child's ongoing care and is entirely voluntary. Guardians will have the opportunity to ask questions to the research team prior to consent being taken. Children will be given a picture to illustrate how a pulse oximeter is used to measure the oxygen saturation levels in the body. The picture has also been designed to provide a colouring-in activity for the child

Healthcare providers:

A member of the research team will approach the ward sister of each inpatient ward with written study information. We will ask for volunteer nurses to take part in the study and arrange in advance a suitable time for this to happen, at the convenience of the nurse and research team. Potential participant nurses will be given information sheets by the research team and have the opportunity to ask questions to the research team prior to consent being taken

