13.3.3 Sensitivity and other planned analyses

We will collect limited data on the number of children in whom we were unable to take measurements, recording their age and clinical condition to compare with those who we were able to take a measurement. We will compare the age distribution between the two groups, to give an indicator of age-bias in successful measurements.

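### No approach order and no record of eligible children passed over: ward staff could favour easier children within an age group, which would probably raise the GOSH proportion within 60 seconds

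*Combined protocol and SAP*

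**What the plan says.** Section 7 states the sampling method: "Recruitment of children will be purposeful; to ensure a range of ages (0-59 months old) are included in the study". The clinical researcher recruits, but the candidates come from ward staff: "We will ask the ward sister to identify patients in the four different age categories who are stable". The sections differ on who first gives the guardian information. Section 7 says "We will ask the ward sister to hand out patient information leaflets to the guardian", while section 8.1 says "the nurse responsible for the patient will make the initial approach to the child and provide the guardian with an information sheet".

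The tested providers come from the same hospital's wards: "We will approach nurses on each ward in the hospital and hand out study healthcare worker information". Eligibility is wide: "Any nurse employed at Great Ormond Street Hospital who is trained to use pulse oximetry will be eligible to participate in the study". No rule says which nurse measures which child.

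Selection is not limited by age alone. Sections 5, 6.1 and 6.2 also require clinical stability as judged by the ward sister and medical team, a guardian present with adequate English, written consent and, in the provider part, a saturation pre-test by the researcher.

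On children without a result, section 13.3.3 says "We will collect limited data on the number of children in whom we were unable to take measurements". Their age and clinical condition are recorded, but the only comparison spelled out is of age distribution.

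**The concern.** Purposive sampling is openly declared and is common in usability work. It needs more care here because the same sample supports a proportion with a 95% confidence interval (section 13.2.1), and section 5 makes 95% within 60 seconds the criterion for calling the device a success.

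The protocol itself ties speed of reading to the child's state. Section 3.3 cites agitated children as an example of where readings take 2 to 15 minutes, and the stopping rule in section 8.4 is framed around a cooperative child. Section 3.4 says oximetry is routine at GOSH at all staff levels, so ward staff may well know which children accept a probe. Age quotas fix the age mix but not the mix of difficulty within an age group.

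If easier children are put forward more often, the observed proportion probably rises. With no record of those passed over, the data could not show whether this happened.

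**Working it through.** **1. The plan's own figure.** Section 13.2.1 gives p = 0.95, e = 0.025 and a 95% interval. With Z = 1.96, n = 1.96² × 0.95 × 0.05 / 0.025² = 291.96, rounded up to 292, so the stated number reproduces. (The printed line puts 0.95 in place of Z, which would give 68.6; the result is right and the substitution is a slip.) Treating measurements as independent, as that formula does, the half-width 1.96 × √(0.95 × 0.05 / n) is 2.1 points for the 408 GOSH measurements and 1.2 points for the pooled 1,224. Selection bias does not shrink as n grows.

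**2. Who is recorded.**
- Measured children: the independent observer notes their condition (section 5).
- Children who could not be measured: number, age and clinical condition (section 13.3.3).
- Eligible children not put forward, not approached or declined: no record is described.

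**3. Illustration of size.** The documents give no rates, so these inputs are assumptions: 20% of eligible children are difficult with 80% success, and 80% are easy with 98% success. Let r be the rate at which difficult children are selected relative to easy ones.

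- Share of difficult children enrolled: s = 0.2r / (0.2r + 0.8)
- GOSH proportion: 0.98 − 0.18s
- Pooled proportion, with GOSH supplying 408 of 1,224 (one third) and the other two sites held at 94.4%: (GOSH + 2 × 0.944) / 3

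| r | s | GOSH alone | Three sites pooled |
|---|---|---|---|
| 1 | 0.20/1.00 = 0.200 | 94.4% | 94.4% |
| 0.75 | 0.15/0.95 = 0.158 | 95.2% | 94.7% |
| 0.5 | 0.10/0.90 = 0.111 | 96.0% | 94.9% |
| 0.25 | 0.05/0.85 = 0.059 | 96.9% | 95.2% |

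The GOSH share is also one third within each user stratum (204 of 612), so the pooled column applies there too. If all three sites selected alike, the pooled figures would equal the GOSH column.

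**4. Other assumed inputs.** Take easy children at 95%, difficult children at 80% and 20% of those eligible. All comers give 0.8 × 0.95 + 0.2 × 0.80 = 92.0%. Passing over half the difficult children gives 0.95 − 0.15 × 0.111 = 93.3%, and passing over all of them gives 95.0%. Keeping easy children at 95% and letting difficult success run from 70% to 90% and their share from 10% to 30%, the GOSH figure rises by 0.2 to 3.1 points if half are passed over and by 0.5 to 7.5 points if all are. Divided by three, the pooled rise is 0.1 to 1.0 and 0.2 to 2.5 points.

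**5. Overlap of nurse and child.** Sections 7 and 8.1 neither bar nor state it. It could arise only in the provider part, which is 204 of the 408 GOSH measurements. Selection by ward staff bears on both parts.

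**The case against.** A reader might infer that a modest under-selection turns a miss into a pass on the primary result. The documents do not support this. Sections 5 and 13.2.1 make the primary analysis a pooled one over three sites, and this protocol governs recruitment only at GOSH. With the other sites unaffected, even r = 0.5 leaves the pooled figure at 94.9%. The crossing at GOSH also depends on a starting point only 0.6 points below target; under the inputs in step 4, halving the selection of difficult children still leaves a miss. This objection stands.

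A reader might also infer that tested nurses choose or measure their own patients. No section says so. Sessions are arranged in advance, and each nurse needs three children in each of four age groups, which limits how many could be in her care. The effect of familiarity could go either way: a child may resist a nurse linked with unpleasant procedures. This stands too, so the overlap is only a permitted possibility.

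Nor is age the only limit on selection. The other eligibility limits are real, and the provider part deliberately uses well or mildly ill children. The comparison that matters is therefore with all eligible children, not all inpatients.

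Finally, case mix among measured children is described, and section 13.3.3 gives some trace of failures. On its natural reading that section does not reach children who were never put forward, not approached or declined. If it was meant to, the text should say so. It is also fair that ward staff would still judge stability under any remedy, so some discretion would remain.

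**Conclusion.** The point holds as a gap in recruitment procedure and record-keeping. Within the eligibility limits, ward staff choose which children are offered, no order is fixed, and those passed over leave no record, so selection on expected ease is possible and could not be detected. An upward bias in the GOSH proportion is the likely direction, but that is an inference.

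The size rests wholly on assumed inputs. On the main illustration, GOSH rises by 0.8, 1.6 or 2.5 points and the pooled figure by about 0.3, 0.5 or 0.8 points, the latter only if the other sites are unaffected. The effect could be negligible or could match the planned 2.5-point precision. The documents do not show that selection of this kind occurs, that it would change the pooled conclusion, or that tested nurses measure their own patients. The remedy is cheap enough that the change should be made.

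**What to change.** In sections 7 and 8.1, keep ward staff judging stability and making the first approach. Have the clinical researcher take the list of all eligible children in the age group and work through it in a pre-stated order, such as bed order, until the quota is filled. Log anonymously the age group and reason for each listed child not approached, declined or screened out, including at the saturation pre-test, and add these counts to section 13.3.3.

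Where practical, assign tested nurses to children not in their care. Otherwise record whether the child was in the nurse's care and report a sensitivity analysis on that basis.

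Reconcile sections 7 and 8.1 on who first gives the guardian information. The saturation limits in sections 5, 6.2 and 8.2 disagree for a child at exactly 95% and must also be reconciled, so that screened-out children are counted consistently.

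The cost is a short wording change, a brief log and slightly less flexible scheduling, with no extra children. If section 13.2.2 means three providers a day taking 12 measurements each, 17 providers need 17 / 3 = 5.7 days of a three-week allowance, which leaves room. Where separating nurses from their own patients would still disrupt a ward, recording the relationship is enough.

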8.1 Informed consent procedure

It is the responsibility of the clinical researcher to obtain written informed consent from each subject prior to participation in the study, following adequate explanation of the aims, methods, anticipated benefits and potential hazards of the study. No study procedure will be conducted prior to taking consent from the participant. Consent will not denote enrolment into the study. The signed consent form will be retained at the study site and a copy placed in the medical notes.

Child participants:

A member of the research team will approach the responsible clinical team for potential participants. Having identified a potential patient, the nurse responsible for the patient will make the initial approach to the child and provide the guardian with an information sheet. Only after this point will a member of the research team then approach the parent to ask for informed consent, provided the parent is happy to be approached, making it clear that participation will have no impact on the child's ongoing care and is entirely voluntary. Guardians will have the opportunity to ask questions to the research team prior to consent being taken. Children will be given a picture to illustrate how a pulse oximeter is used to measure the oxygen saturation levels in the body. The picture has also been designed to provide a colouring-in activity for the child

Healthcare providers:

A member of the research team will approach the ward sister of each inpatient ward with written study information. We will ask for volunteer nurses to take part in the study and arrange in advance a suitable time for this to happen, at the convenience of the nurse and research team. Potential participant nurses will be given information sheets by the research team and have the opportunity to ask questions to the research team prior to consent being taken

8.2 Baseline assessments

All children will be assessed for their age and clinical condition; children who are critically unwell will not be included in the study. Children with oxygen saturations of <95% will not be measured by the healthcare providers.

8.3 Definition of end of study

The study will be completed at the end of recruitment. There will not be any follow-ups of the healthcare providers or children involved in the study. We anticipate the recruitment to take a maximum of 4 weeks.

8.4 Discontinuation/withdrawal of participants and 'stopping rules'

The study will stop recruitment if the first 25 readings obtained by the expert user are deemed unreliable according to clinical criteria (i.e. unable to obtain a stable oxygen saturation reading within 5 minutes of application of the probe in a cooperative child). In this situation the redesigned probe and oximeter will be considered 'unusable'.

9 Name and description of Investigational Device

The study involves the use of the AH-MX pulse oximeter manufactured by Acare Technology Co Ltd (Taiwan), and a new prototype pulse oximeter probe manufactured for use with the AH-MX pulse oximeter, the Lifebox A2 pulse oximeter probe (MHRA Class 11b device).

Pulse oximeters are comprised of two parts: the oximeter monitor and the oximeter probe. There is no change in the intended use of the pulse oximeter.

1. The AH-MX Pulse Handheld Pulse Oximeter monitor

The existing Lifebox pulse oximeter is the AH-MX Handheld Pulse Oximeter manufactured by Acare Technology Co Ltd in Taiwan.

The AH-MX handheld pulse oximeter is intended for continuously monitoring or spot checking peripheral oxygen saturation (SpO₂) and pulse rate (PR) for adult, paediatric or neonatal patients. This device can be used in institutions or units with health care capability. This includes outpatient departments, emergency rooms and departments of internal medicine in hospitals, ordinary departments in clinics, nursing hospitals and community medical institutions. It may also be used in the home.

The AH-MX pulse oximeter has been CE marked according to the following safety standards:

Safety: IEC 60601-1:2012-Ed.3.1 (EN 60601-1:2006/A1:2013)

EMC: IEC 60601-1-2:2007-Ed.3.0 (EN 60601-1-2:2007/AC:2010)

Pulse Oximeter consensus standard: (EN)ISO 80601-2-61:2011

Modifications to the AH-MX Pulse Oximeter

The AH-MX pulse oximeter monitor has been modified for this project (AH-MX v3)

There have been no changes to the hardware of the oximeter. The oximeter will be powered by 3 commercially available AA alkaline batteries for the study. There has been no change to the intended use of the oximeter

The software in the AH-MX oximeter has been upgraded to allow the oximeter to respond more quickly and more reliably at low perfusion in children 0-59 months. No oxygen saturation readings will be taken for clinical care during the study and there are no safety hazards associated with the upgraded software in this device.

2. Lifebox A2 Pulse oximeter probe

The project team has designed a new prototype pulse oximeter probe for children 0-59 months (the Lifebox A2 probe), intended for use with the AH-MX pulse oximeter. This probe is the focus of this usability testing study. The probe has been designed to fit on the foot of infants, and the finger of older children and adults.

The Lifebox pulse oximeter prototype probes are manufactured with the intent to make them suitable for human use. The materials chosen are all currently in use as part of FDA and ISO cleared devices. The outer shell is of a polycarbonate / acrylonitrile butadiene styrene (ABS) blend and the pads are silicone. These materials are identical to those used in the Nellcor DS100a which has been in use globally for 25 years. The cable jacket is made of a polyurethane that has been FDA cleared and met ISO requirements in the Envisen Bridge FQ series of sensors which are also sold under EnviteC and Bluepoint brands.

While the prototypes as assembled have not yet been subjected to a biocompatibility test, historical experience is that if only known biocompatible materials are used, the device will meet the requirements.

Electrical safety of the sensors in all pulse oximeters is provided in the monitor. For the purpose of the study at GOSH the oximeter will be powered by 3 commercially available AA alkaline batteries.

10 Recording and reporting of adverse events and reactions

10.1 Definitions

Term	Definition
Adverse Event (AE)	Any untoward medical occurrence in a patient or clinical trial subject where the trial medical device is used and which does not necessarily have a causal relationship with this treatment.
Adverse Reaction (AR)	Any untoward and unintended response in a subject where the trial medical device is used, which is related to the medical device. This includes uses outside of protocol (including misuse and abuse of product)
Serious adverse event (SAE), serious adverse reaction (SAR) or unexpected serious adverse reaction	Any adverse event, adverse reaction or unexpected adverse reaction, respectively, that: 
 • results in death • is life-threatening • requires hospitalisation or prolongation of existing hospitalisation • results in persistent or significant disability or incapacity • consists of a congenital anomaly or birth defect
Important Medical Event	These events may jeopardise the subject or may require an intervention to prevent one of the above characteristics/consequences. Such events should also be considered 'serious'.
Unexpected adverse reaction	An adverse reaction the nature and severity of which is not consistent with the information about the device in question set out in the investigator's brochure relating to the trial in question.

SUSAR	Suspected Unexpected Serious Adverse Reaction
-------	---

10.2 Recording adverse events

All adverse events will be recorded in the child's medical records following consent. If the clinical researcher suspects that the subjects' clinical condition has been affected by the oxygen saturation measurement, then they will record and report this as an unexpected adverse event. All adverse events will be recorded with clinical symptoms and accompanied with a simple, brief description of the event. All adverse events will be recorded until the oxygen saturation observation is completed.

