Study duration per participant:	Healthcare providers are the main study participants and will be involved in the study between 1 and 4 hours, with each healthcare provider taking 12 oxygen saturation measurements.
	Children will be involved in the study intermittently for up to 80 minutes. Children will be assessed for recruitment and consented prior to each measurement.
Estimated total study duration:	4 weeks
Planned study sites:	Great Ormond Street Hospital [single-site]
Total number of participants planned:	17 healthcare providers, and up to 408 children aged 0-59 months
Main inclusion/exclusion criteria:	The study will be conducted in the inpatient wards of Great Ormond Street Hospital, with recruited healthcare providers and children aged 0-59 months. Inclusion: 
- Children aged 0-59 months in an inpatient ward at Great Ormond Street Hospital- Healthcare provider working on an inpatient ward at Great Ormond Street Hospital Exclusions: 
- Children aged >59 months- Children in critical condition- Guardians lacking capacity to give informed consent for their child- Guardians unable to speak English
Statistical methodology and analysis:	We will calculate the proportion of readings that meet the target product profile requirement of 95% stable readings within 60 seconds. We will describe the time to stable reading, looking at the median time and inter-quartile range. We will compare these descriptive statistics between patient age groups, expert and healthcare provider participants, and with measurements from sites in Malawi and Bangladesh. We will describe differences between these sub-groups using t-tests. Qualitative questionnaire data will be analysed using an inductive thematic approach.

3 Introduction

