10.2.1 Severity

Category	Definition
Mild	The adverse event does not interfere with the volunteer's daily routine, and does not require intervention; it causes slight discomfort
Moderate	The adverse event interferes with some aspects of the volunteer's routine, or requires intervention, but is not damaging to health; it causes moderate discomfort
Severe	The adverse event results in alteration, discomfort or disability which is clearly damaging to health

10.2.2 *Causality*

The assessment of relationship of adverse events to the pulse oximetry measurement is a clinical decision based on all available information at the time of the completion of the measurement. The following categories will be used to define the causality of the adverse event:

Category	Definition
Definitely:	There is clear evidence to suggest a causal relationship, and other possible contributing factors can be ruled out.
Probably:	There is evidence to suggest a causal relationship, and the influence of other factors is unlikely
Possibly	There is some evidence to suggest a causal relationship (e.g. the event occurred within a reasonable time after administration of the trial medication). However, the influence of other factors may have contributed to the event (e.g. the patient's clinical condition, other concomitant events).
Unlikely	There is little evidence to suggest there is a causal relationship (e.g. the event did not occur within a reasonable time after administration of the trial medication). There is another reasonable explanation for the event (e.g. the patient's clinical condition, other concomitant treatments).
Not related	There is no evidence of any causal relationship.
Not Assessable	Unable to assess on information available.

10.2.3 *Expectedness*

Category	Definition
Expected	An adverse event that is classed in nature as serious and which is consistent with the information about the pulse oximeter and probe listed in the Investigator Brochure or clearly defined in this protocol.
Unexpected	An adverse event that is classed in nature as serious and which is not consistent with the information about the pulse oximeter and probe in the Investigator Brochure

10.2.4 *Seriousness*

Seriousness as defined for an SAE in section 10.1. Collection, recording and reporting of adverse events (including serious and non-serious events and reactions) to the sponsor will be completed according to the sponsor's guidelines.

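### Adverse-event recording stops when the reading is completed and no probe-site check is planned, so non-serious skin reactions first seen at or after probe removal would not be systematically captured

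*Combined protocol and SAP*

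**What the plan says.** Four parts of the protocol bear on this point.

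- **Recording window.** Section 10.2 starts recording in the child's medical records after consent and closes it as follows: "All adverse events will be recorded until the oxygen saturation observation is completed". It also asks the clinical researcher to record and report any suspected effect of the measurement on the child.
- **Causality.** Section 10.2.2 (printed under the heading for assessment of adverse events) calls the causality judgement "a clinical decision based on all available information at the time of the completion of the measurement". Its *Possibly* grade gives as an example that "the event occurred within a reasonable time after administration of the trial medication", and the *Unlikely* grade uses the reverse.
- **Follow-up.** Section 8.3 states: "There will not be any follow-ups of the healthcare providers or children involved in the study".
- **The device.** Section 9, on the Lifebox A2 probe, says that "the prototypes as assembled have not yet been subjected to a biocompatibility test". The same section gives a mitigation. The shell and pad materials match those of a probe in global use for 25 years, the cable jacket material is already cleared, and past experience is that known materials meet the requirements.

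Section 3.4 classes the study as Type A and states that the measurement carries no risk. Section 4 asks whether children tolerate the probe well, and 13.1.2 lists tolerance as a secondary outcome. Section 13.3 describes no tabulation of adverse events and no analysis of tolerance by name.

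**The concern.** A local skin reaction under a probe may show only when the probe comes off, or some time later. The plan closes recording at about the moment when such a reaction could first be seen, and it schedules no inspection of the site. The assembled prototype has not been tested for biocompatibility, so the study is an opportunity to check the expectation about its materials in up to 408 children at this site. As written, that opportunity is largely not taken.

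What is at stake is how a low or zero count of reactions can be read. It could be presented as good tolerance, and as agreement with the no-risk statement, when the recording rule was not built to detect the relevant events. The results are also to be pooled with those from Malawi and Bangladesh (section 3.3), so a weak safety denominator from this site would be carried into the pooled report.

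**Working it through.** The plan states no figure on this point, so there is none to reproduce. The check has two parts.

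**1. The passages side by side.** Section 5 ends a successful reading when the user calls stop at a stable waveform. Section 10.2 does not say whether the observation ends there or includes taking the probe off.

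- If it ends at the stop call, a mark seen on removal is already outside the window.
- If it includes removal, a mark seen on removal is inside the window, but no one is told to look for it, and anything that appears later is outside.

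On either reading, a non-serious reaction that appears after removal has no planned route into the data. The expedited route for serious events starts when the chief investigator becomes aware of the event and has no end date, but it covers serious events only. The stopping rule in 8.4 concerns readings that cannot be obtained, not harm.

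The causality wording needs reconciling too. The grades ask how long after exposure the event arose, while the assessment is fixed at completion of the measurement. An event can follow probe placement and still precede completion, so this is not a flat contradiction. It does leave little room for the timing criterion to be used.

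**2. What a low count would mean (illustration).** Inputs: n = 408 children, from the Summary. The true reaction rate p and the share f of reactions visible by the end of the reading are assumptions; the documents give neither. Children are treated as independent.

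Chance of recording at least one reaction = 1 − (1 − p·f)^408.

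| f | p = 0.5% | p = 1% | p = 2% |
|---|---|---|---|
| 1 | 87.1% | 98.3% | >99.9% |
| 0.5 | 64.0% | 87.1% | 98.3% |
| 0.25 | 40.0% | 64.0% | 87.1% |
| 0.1 | 18.5% | 33.5% | 55.8% |
| 0 | 0% | 0% | 0% |

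For example, with p = 1% and f = 0.1: 1 − (1 − 0.001)^408 = 33.5%.

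If no reaction is recorded in 408 children, the exact one-sided 95% upper bound is 1 − 0.05^(1/408) = 0.73%. That bound applies to p·f, the rate of reactions visible before recording stops. Dividing by f gives the bound on the full rate p: 0.73%/0.5 = 1.5%, 0.73%/0.25 = 2.9%, 0.73%/0.1 = 7.3%. With f = 0 there is no bound.

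**The case against.** The case against is substantial, and much of it stands as a limit on the point.

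- **Other routes exist.** The children are inpatients or awaiting surgery, with a guardian present at recruitment, and events go into their medical records. The sentence in 10.2 about the researcher's suspicion has no end time of its own. Section 10.2.4 refers collection and reporting to sponsor guidelines that are not part of the document, and a longer window there cannot be excluded. A reader might infer that delayed reactions cannot be found at all. The documents support only that they would not be systematically captured.
- **The 80 minutes.** The Summary says: "Children will be involved in the study intermittently for up to 80 minutes". A reader might infer that the child remains in the study well after recording stops. The next sentence, "Children will be assessed for recruitment and consented prior to each measurement", shows that screening and consent use part of that time, and all of it may fall before the last reading ends. The window also opens at consent, so its length is not the time of one reading. No fraction of the 80 minutes can be calculated from the text.
- **Seriousness.** A reader might infer that fixing the assessment at completion also defeats the seriousness criteria, such as prolonged hospitalisation. It does not: 10.2.4 sets no time point, and serious events are reported on awareness.
- **Pressure injury.** The target is a reading within 60 seconds. The 5 minutes in 8.4 defines an unreliable reading and does not cap contact. Nothing in the documents points to pressure injury, so skin irritation is the better example.
- **Low prior risk.** The materials are known and the study is classed as Type A. This lowers the expected rate, but it is an expectation about components and not data on the assembled probe.
- **Tolerance is already observed.** An observer notes the child's condition, and tolerance and fit are secondary outcomes. No passage says that this includes the skin under the probe.

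**Conclusion.** The point holds in a limited form. Recording and causality assessment end with the measurement, follow-up is excluded, and no probe-site check is scheduled for a prototype that is untested for biocompatibility as assembled. Non-serious probe-site reactions first visible at or after removal would therefore not be systematically captured, and few recorded reactions would be weak evidence of tolerance or absence of risk.

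The size cannot be fixed from the documents, because it depends on how many reactions show before recording stops. In the illustration, the gap is negligible if nearly all do and large if few do. The conclusion assumes that the unseen sponsor guidelines do not already extend the window.

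The primary outcome and the sample size are not affected. This is a worthwhile and inexpensive repair to the safety data, not a flaw that undermines the study.

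**What to change.** 1. **Section 10.2:** state that recording runs from consent through probe removal. Include a look at the probe site at removal by the observer already present, entered in one field on the tablet form. Include any probe-site reaction that ward staff or the guardian later report to the team.
2. **Section 10.2.2:** allow causality to be assessed or updated on the information available when the event is reported. Replace the drug-trial wording in the grades with wording about probe contact, so that the timing criterion and the time of assessment agree.
3. **Section 8.3:** make clear that accepting later-reported reactions is compatible with having no scheduled follow-up.
4. **Reporting:** give the count of probe-site reactions, with the number of children checked, alongside the existing tolerance outcome. State that the count covers reactions seen up to removal plus those reported later.

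The cost is protocol wording, one form field and a few seconds per child. Later reports will still depend on someone noticing and telling the team. A next-day review of the notes would reduce that dependence, but it is optional. Section 7 uses the notes only for basic demographic data, so a review would need added protocol and consent wording, and it would be incomplete for children discharged the same day.
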